6.5 Adjustment for covariates

Not applicable.

6.6 Handling of dropouts and missing data

No imputation algorithms will be adopted to replace missing values.

In all listings, missing or incomplete dates should be left as they have been recorded. However, for calculation / sorting / assignation based on dates, the following methods will be used:

- 1) The most conservative approach will be systematically considered (i.e. if the onset date of an AE/concomitant medication is missing/incomplete, it is assumed to have occurred

during the study treatment phase (i.e. a TEAE for AEs) except if the partial onset date or other data [stop date,...] indicates differently).

- 2) A missing/incomplete date of medical history or disease diagnosis will be assumed to have occurred before any study treatment.
- (3) In the event that any date is incomplete after Data Management processing and this date needs to be used for calculation (eg. time since primary diagnosis), the following will be assigned for the incomplete date:

- if no field is available: no imputation will be performed.
- if only the year is available: Day "01" and month of "July" will be imputed.
- if the month and year are available: Day "15" will be imputed.

6.7 Multicentre studies

Not applicable.

6.8 Examination of subgroups

For both co-primary efficacy variables (ALSFRS-R and FVC), subgroup analysis will be performed, based on Riluzole use (yes or no) and site of onset (limb-onset or bulbar onset).

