4. SELECTION OF STUDY POPULATION

Subjects of both genders who are older than 18 years of age and younger than 70, who have an ALS diagnosis, and who give their consent to participate after having been duly provided signed informed consent by the investigator may be included in this study.

Both untreated subjects and subjects on a stable dose of Riluzole for at least 28 days may be enrolled.

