5.3. Permitted concomitant treatments

The subject may continue receiving his/her usual medication.

The permitted treatments shall be those necessary from the point of view of the investigator.

In particular, the administration of Riluzole may be considered at a dose of 1 tablet of 50 mg in the morning and 1 tablet of 50 mg at night (2 tablets per day, one every 12 hours). The administration of Riluzole should be avoided immediately before and after the PE.

All medication administered during the study will be considered as concomitant medication and must be recorded in the case report form (CRF).

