1 INTRODUCTION

This Statistical Analysis Plan (SAP) is based on Clinical Study Protocol (CSP) Version 2.0, dated May 5th, 2016, and the SAP of the IG1309 study.

Amyotrophic Lateral Sclerosis (ALS) is an adult-onset paralyzing, rapidly progressive neurodegenerative disease that affects the upper and lower motor neurons. It is characterized by the loss of motor neurons in the cerebral cortex, brainstem and anterior horn of the spinal cord. ALS manifests itself with motor deficits, muscle atrophy, and difficult in breathing, and it is often accompanied by difficulty in swallowing.

ALS is the motor neuron disease with the worst prognosis, with an average survival after diagnosis that falls between 2 and 5 years, and 60% of patients dying within the 3 years (1,2). Death of ALS patients is usually produced by respiratory failure (3).

Two types of ALS are predominantly distinguished by their onset: limb-onset ALS which begins with motor impairments of the extremities, and bulbar-onset ALS with motor impairments at the level of the cranial nerves (4).

ALS continues to be a devastating neurodegenerative disease with an uncertain pathogenesis, for which no cure exists. There have not been any precise biomarkers identified for the disease, and diagnosis is established through clinical manifestations and neuronal damage evaluated through electromyography (EMG).

Current treatment for this disease is related to excitotoxicity control, which has limited results with regard to the prognosis (5). The first drug approved for its treatment is Riluzole, a glutamate release inhibitor, which lengthens life expectancy by 2 to 4 months in patients with moderate functional impairment (6-7). More recently Radicava® (edaravone) was approved by FDA in 2017 and is the only new FDA-approved treatment option for ALS in the last 20 years shown to slow disease progression (8). It is a free radical scavenger, although the precise mechanism is unknown (9). Accordingly, the majority of interventions aimed at delaying the progression of the disease are at the symptomatic and/or palliative level. In this sense, care which helps preserve the quality of the subject's life is especially important and is mainly achieved via respiratory and nutritional support (10).

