3.3 Determination of sample size

There has been no formal calculation for the sample size since this is a pilot study. The number of subjects planned to be included in this study is 10 subjects completing the planned treatment. The sample size is considered adequate for the evaluation of the objectives of the study. In addition, there is a rising consensus in the ALS field that active control group comparisons should be avoided in early trials (19).

Lastly, the current EMA guidance document, *Guideline on clinical investigation of medicinal products for the treatment of amyotrophic lateral sclerosis (ALS) (EMA/CHMP/4015/2013)* states that the average functional decline is about 1 point per month in untreated subjects on the ALSFRS-R Functional Scale (20). Thus, it may be assumed that 10 subjects followed during 1 year of the clinical trial would be sufficient to evaluate a change of disease progression rate. In the event that a move towards stabilization is observed, the subsequent confirmatory studies will require a formal calculation for the sample size.

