6.4 Level of significance, multiple comparisons and multiplicity

If applicable, all statistical tests will be 2-sided and will be performed using a 5% significance level.

No adjustment for multiple comparisons or corrections for multiplicity are planned.

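### ALSFRS-R decline is compared with an untreated-patient rate, but ALS drugs may be started on study and the only drug analysis is an untimed Riluzole yes/no split, so another drug's slowing could be credited to plasma exchange

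*SAP*

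**What the plan says.** **The comparison.** SAP 6.3.4 compares the observed overall ALSFRS-R change from baseline with an expected loss of 1 point per month, by a one-sample t-test or a signed-rank test. SAP 3.3 gives the source of that rate: "average functional decline is about 1 point per month in untreated subjects". SAP 1 counts the treatment as efficacious when a subject declines more slowly than expected, and sets no condition about other drugs. SAP 6.4 adds that "all statistical tests will be 2-sided and will be performed using a 5% significance level".

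**Other ALS drugs.** At entry, "Both untreated subjects and subjects on a stable dose of Riluzole for at least 28 days may be enrolled" (protocol 4). After entry, protocol 5.3 lets usual medication continue, says that Riluzole may be considered, and leaves the rest open: "The permitted treatments shall be those necessary from the point of view of the investigator". Protocol 1.1 describes Riluzole as the only approved drug. The SAP, dated 29 April 2019, updates this. It reports the 2017 approval of edaravone and calls it "the only new FDA-approved treatment option for ALS in the last 20 years shown to slow disease progression".

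**The analysis.** SAP 6.8 keeps the protocol's split: "For both co-primary efficacy variables (ALSFRS-R and FVC), subgroup analysis will be performed, based on Riluzole use (yes or no) and site of onset". SAP 6.5 plans no covariate adjustment. SAP 6.3.7 tabulates prior and concomitant medication, and Appendix 1 lists them by subject.

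**The concern.** A single-arm study takes its contrast from the external rate. A subject who starts a drug that slows progression no longer follows the untreated course, yet every later visit still enters the test against 1 point per month. Any such effect pushes the result towards slower decline than expected, which is the SAP's sign of efficacy, and it accumulates with time on the drug.

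Between protocol version 2.0 (May 2016) and the SAP, the background section took in a second approved drug, but the analysis did not. Because SAP 6.8 does not say whether Riluzole use means use at baseline, use started on study, or use at any time, even the one planned drug analysis has no fixed meaning.

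**Working it through.** The plan has no figure to reproduce. SAP 3.3 states: "There has been no formal calculation for the sample size since this is a pilot study". The check therefore has two parts: whether any rule in the documents closes the gap, and how large the bias could be.

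**1. Does another rule close the gap?**
- Exclusion criterion 3 concerns investigational-product studies before screening, not an approved drug started later.
- The 28-day Riluzole condition applies at enrolment only.
- Withdrawal criterion 6 concerns a concomitant disease or medical condition.
- The per-protocol set removes major deviations (SAP 5.3). A drug allowed under protocol 5.3 is not plainly a deviation.

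None of these handles an ALS drug started on study.

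**2. Expected untreated decline.** At 1 point per month, decline = weeks × 7 / 30.4375 (the SAP's own month length).
- Week 12: 2.76
- Week 25: 5.75
- Week 48: 11.04

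**3. Apparent benefit when plasma exchange has no effect.**

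Bias = share of subjects × proportional slowing × points expected after the drug is started.

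Assumed, not in the documents: 2 to 5 of 10 subjects start at Week 12 and then decline 20 to 40% more slowly.
- Week 25: 5.75 − 2.76 = 2.99 points remain. Bias is 0.2 × 0.2 × 2.99 = 0.12 to 0.5 × 0.4 × 2.99 = 0.60.
- Week 48: 11.04 − 2.76 = 8.28 points remain. Bias is 0.2 × 0.2 × 8.28 = 0.33 to 0.5 × 0.4 × 8.28 = 1.66.

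For a drug taken throughout, the Week 48 bias is 0.5 × 0.20 × 11.04 = 1.10 (20% slowing in half the subjects) or 0.5 × 0.33 × 11.04 = 1.82 (33% slowing in half).

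**4. Chance of a significant result in the favourable direction at Week 48.** One-sample t-test, n = 10, two-sided 5%, noncentrality = bias / SD × √10. The SD of the change is not in the documents; 4 to 8 points is assumed.

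| Bias (points) | SD 8 | SD 6 | SD 4 |
|---|---|---|---|
| 0 | 2.5% | 2.5% | 2.5% |
| 0.33 | 3.3% | 3.6% | 4.2% |
| 1.10 | 5.8% | 7.5% | 12.0% |
| 1.66 | 8.5% | 12.0% | 21.6% |
| 1.82 | 9.4% | 13.6% | 25.1% |

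The 2.5% in the first row holds only if 1 point per month is the true untreated rate for these subjects.

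**5. Could the planned subgroup tables show it?** With an assumed 5/5 Riluzole split, the 95% confidence half-width for a subgroup mean is 2.776 × SD / √5, or 5.0 to 9.9 points. That is several times the bias, so they could not.

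**The case against.** The strongest reply is that this is a pilot without a control group. Protocol 11.2 calls the evaluation descriptive, SAP 3.3 defers formal sizing to later confirmatory studies, and any comparison with an external rate has an attribution limit. The 95% half-width for the mean of all 10 subjects is about 2.9 to 5.7 points at the assumed SDs, wider than the whole 0.33 to 1.66 range. This stands as a limit on how much the point can matter. It does not remove the point, because the SAP adds 5% tests and an efficacy criterion, and the bias has a known direction.

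A reader might also infer more than the documents support:
- **That the bias has occurred.** Nothing shows that any subject took edaravone or started Riluzole on study, and no enrolment dates are given.
- **That FVC is affected in the same way.** FVC is tested only against baseline. The untreated-rate argument applies to overall ALSFRS-R alone.
- **That Riluzole is known to slow ALSFRS-R decline.** The documents credit it with 2 to 4 months of life expectancy and give no effect on slope. Only edaravone is described as slowing progression.
- **That a subject starting Riluzole mid-study is counted as a user at visits before the start.** This is one reading of SAP 6.8. A baseline reading is at least as natural, since the entry rule contrasts untreated with stable-dose subjects. The defect is the undefined term.
- **That these drugs would be seen only in a summary table.** Individual listings of medication, ALSFRS-R and FVC are planned, and 10 subjects can be read side by side. But no planned analysis links them.

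Leaving out visits after a drug start is itself selective. If faster decliners start new drugs, the visits that remain favour slower decliners. This objection stands and determines the form of the fix.

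**Conclusion.** The point holds as a gap in the analysis plan. SAP 6.3.4 uses an untreated-patient rate, the protocol permits ALS drugs to be started on study, the SAP names one that slows progression, and its only drug-related efficacy analysis is an untimed Riluzole split. Slowing from edaravone or newly started Riluzole could then be attributed to plasma exchange.

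The textual gap is certain; its size is not. Under the assumed shares and slowing for drugs started at Week 12, the Week 48 bias is 0.33 to 1.66 points, or 3 to 15% of the expected 11.04. With assumed SDs of 4 to 8, the chance of a falsely favourable test rises from 2.5% to between 3.3% and 21.6%. With few users or a weak effect it is minor, and with none it is zero. The change is worth making because it is cheap and bears on what a favourable result can be said to show.

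**What to change.** 1. **SAP 6.8:** define Riluzole use by status at PE#1.
2. **SAP 6.3.4:** add a sensitivity analysis of the ALSFRS-R comparison with 1 point per month. Leave out subjects on edaravone at PE#1, and each subject's visits after the first dose of edaravone or of newly started Riluzole. Report it beside the main result with the number of subjects affected, and flag those subjects and visits in the individual ALSFRS-R listing.
3. **Interpretation:** state in advance that, if the two results differ, slower-than-expected decline is not attributed to plasma exchange alone.
4. **FVC:** the baseline comparison may be repeated the same way, as supportive only.

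This should stay a sensitivity analysis and not become a condition for the efficacy statement, because of the possible selection and because few observations may remain. It also does not make subjects already on Riluzole at PE#1 untreated. They remain in both analyses, and the report should say so.

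The cost is a few lines of SAP text, one rerun of the ALSFRS-R table and a flag in a listing. Protocol 5.3 already has all medication recorded in the CRF, and SAP 6.3.7 already needs dates relative to PE#1. No treatment rule changes.

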6.9 Interim analysis

No interim analysis will be performed.

6.10 Data monitoring

Not applicable.

8 APPENDIX 1 – DATA PRESENTATION PLAN

8.1 Tables to be produced for the Clinical Study Report (Section 14 according to ICH E3)

Demographic and baseline characteristics

Table 14.1.1 Inclusion and exclusion criteria – Enrolled Population

Table 14.1.2 Disposition of subjects – Enrolled Population

Table 14.1.3 Reason for exclusion from population – Enrolled Population

- Table 14.1.4 Demographics data – Safety Population
- Table 14.1.5 ALS Medical history – Evaluable Population
- Table 14.1.6 Relevant medical/surgical history – Safety Population
- Table 14.1.7 Pregnancy test – Safety Population
- Table 14.1.8 Peripheral venous access assessment – Evaluable Population

Primary Efficacy analysis

- Table 14.2.1.1 ALS Functional Rating Scale by visit – Evaluable population.
- Table 14.2.1.2 ALS Functional Rating Scale by visit – Per-Protocol population.
- Table 14.2.1.3 ALS Functional Rating Scale by visit and Riluzole use – Evaluable population.
- Table 14.2.1.4 ALS Functional Rating Scale by visit and Riluzole use – Per-Protocol population.
- Table 14.2.1.5 ALS Functional Rating Scale by visit and site of onset – Evaluable population.
- Table 14.2.1.6 ALS Functional Rating Scale by visit and site of onset – Per-Protocol population.
- Table 14.2.2.1 Pulmonary function by visit – Evaluable population.
- Table 14.2.2.2 Pulmonary function by visit – Per-Protocol population.
- Table 14.2.2.3 Pulmonary function by visit and Riluzole use – Evaluable population.
- Table 14.2.2.4 Pulmonary function by visit and Riluzole use – Per-Protocol population.
- Table 14.2.2.5 Pulmonary function by visit and site of onset – Evaluable population.
- Table 14.2.2.6 Pulmonary function by visit and site of onset – Per-Protocol population.

Secondary Efficacy analysis

- Table 14.2.3.1 Electromyography: sensory NCS – Evaluable Population
- Table 14.2.3.2 Electromyography: motor NCS – Evaluable Population
- Table 14.2.4.1 ALS Assessment Questionnaire 40 (ALSA Q40): raw scores – Evaluable Population
- Table 14.2.4.2 ALS Assessment Questionnaire 40 (ALSA Q40): transformed scores – Evaluable Population
- Table 14.2.5 ALS Cognitive Behavioral Screen (ALS-CBS) – Evaluable Population
- Table 14.2.6 CSF biomarkers (cytokine panel, neurofilament analysis, BMAA levels) – Evaluable Population
- Table 14.2.7 Changes in the plasma biomarkers before and after selected PE – Evaluable Population

Adverse events

- Table 14.3.1.1 Summary of non-TEAEs – Safety Population
- Table 14.3.1.2 Summary of TEAEs – Safety Population
- Table 14.3.1.3 PE sessions temporarily associated with AR, occurring during or within 72 hours after the completion of the product infusion – Safety Population
- Table 14.3.1.4 PE sessions associated with TEAE, occurring during or within 72 hours after the completion of the product infusion – Safety Population
- Table 14.3.1.5 TEAEs: MedDRA coding by SOC and PT – Safety Population
- Table 14.3.1.6 TEAEs: MedDRA coding by severity, SOC and PT – Safety Population
- Table 14.3.1.7 TEAEs: MedDRA coding by causality, SOC and PT – Safety Population
- Table 14.3.1.8 TEAEs: MedDRA coding by seriousness, SOC and PT – Safety Population

List of deaths and other serious adverse events

- Table 14.3.2.1 Adverse events leading to death – Enrolled Population
- Table 14.3.2.2 Adverse events leading to discontinuation from the study – Enrolled Population
- Table 14.3.2.3 Serious adverse events – Enrolled Population

Laboratory data

- Table 14.3.3.1 Complete Blood Count: absolute values and change from baseline by visit – Safety Population
- Table 14.3.3.2 Complete Blood Count: summary of shift of values by visit – Safety Population
- Table 14.3.3.3 Biochemistry and Lipid Profile: absolute values and change from baseline by visit – Safety Population
- Table 14.3.3.4 Biochemistry and Lipid Profile: summary of shift of values by visit – Safety Population
- Table 14.3.3.5 Serum Electrolytes: absolute values and change from baseline by visit – Safety Population
- Table 14.3.3.6 Serum Electrolytes: summary of shift of values by visit – Safety Population
- Table 14.3.3.7 Coagulation: absolute values and change from baseline by visit – Safety Population
- Table 14.3.3.8 Coagulation: summary of shift of values by visit – Safety Population
- Table 14.3.3.9 Fibrinogen: absolute values and change from baseline by visit – Safety Population
- Table 14.3.3.10 Fibrinogen: summary of shift of values by visit – Safety Population
- Table 14.3.3.11 Serology results by visit – Safety Population

Concomitant therapy

Table 14.3.4.1 Prior medication – Safety Population
Table 14.3.4.2 Concomitant medication – Safety Population

Other safety data

Table 14.3.5.1 Vital signs during evaluation visits: absolute and change from baseline values by visit – Safety Population
Table 14.3.5.2 Vital signs during PE: change from pre-PE assessments – Safety Population
Table 14.3.5.3 Pulse oximetry during PE: change from pre-PE assessment – Safety Population
Table 14.3.5.4 Plasma exchanges by visit – Safety Population
Table 14.3.5.5 Number of PEs received during the study – Safety Population
Table 14.3.5.6 CSF standard analysis: absolute values and change from baseline by visit – Safety Population
Table 14.3.5.7 CSF standard analysis: abnormalities by visit – Safety Population

Other relevant data

Table 14.3.6 Physical examination by visit – Safety Population
Table 14.3.7 Neurological examination by visit – Evaluable Population

8.2 Graphs (Section 14.2-14.3 in ICH E3)

Figure 14.4.1 ALS Functional Rating Scale by visit – Evaluable population.
Figure 14.4.2 ALS Functional Rating Scale by visit – Per-Protocol population.
Figure 14.4.3 Pulmonary function by visit – Per-Protocol population.
Figure 14.4.4 Pulmonary function by visit – Evaluable population.
Figure 14.4.5 Past assessment of ALSFRS-R scores – Evaluable Population
Figure 14.4.6 Past assessment of FVC scores – Evaluable Population

8.3 Listings of individual subject data and other information to be produced for the Clinical Study Report (Sections 16.1 and 16.2 according to ICH E3)

16.2.1. Discontinued subjects.

16.2.1.1 Study termination
16.2.1.2 Treatment termination
16.2.1.3 Subject discontinuation
16.2.1.4 Visit dates

16.2.2. Protocol deviations.

16.2.2 Protocol deviations

16.2.3. Subjects excluded from the analysis.

16.2.3 Subjects excluded from any analysis population

16.2.4. Demographic data.

16.2.4.1 Demographic data
16.2.4.2 ALS Medical history
16.2.4.3 Relevant medical/surgical history
16.2.4.4 Pregnancy test
16.2.4.5 Past assessment of primary endpoints
16.2.4.6 Peripheral venous access assessment
16.2.4.7.1 Inclusion and exclusion criteria
16.2.4.7.2 Eligibility

16.2.5. Individual efficacy response data.

16.2.5.1 ALS Functional Rating Scale
16.2.5.2 Pulmonary function data
16.2.5.3 Electromyography: sensory NCS
16.2.5.4 Electromyography: motor NCS
16.2.5.5 ALSA Q-40 data
16.2.5.6 ALS Cognitive Behavioral Screen (ALS-CBS) data
16.2.5.7 Plasma biomarkers collection
16.2.5.8 CSF biomarkers collection

16.2.6. Adverse events.

16.2.6.1 Adverse events

16.2.7. Individual laboratory measurements.

16.2.7.1 Complete Blood Count measurements data
16.2.7.2 Biochemistry measurements data
16.2.7.3 Serum Electrolytes measurements data
16.2.7.4 Coagulation measurements data
16.2.7.5 Fibrinogen measurements data

16.2.7.6 Serology measurements data

16.2.8. Vital signs and Pulse Oximetry

16.2.8.1 Vital signs

16.2.8.2 Pulse Oximetry

16.2.9. Concomitant medications.

16.2.9.1 Prior medications

16.2.9.2 Concomitant medications

16.2.10. Other relevant data.

16.2.10.1 Plasma exchange

16.2.10.2 Physical examination

16.2.10.3 Neurological examination

16.2.10.4 CSF standard analysis data
